17.1.2. Definition of Opioid Dose

Baseline opioid dose will be defined as the total weekly opioid dose that the subject reports taking during the week prior to study entry (7 days ending in EVAL 1). This value will be used to calculate the opioid doses for each Phase. If a subject reports taking a different opioid dose than instructed during an Assessment Period, the actual subject-reported opioid dose will be used to calculate the efficacy endpoints. In cases where a subject is taking multiple opioids concurrently, the morphine milligram equivalent (MME) will be used to standardize the baseline opioid dose, to calculate the opioid dose for each Phase, and to calculate opioid dose for the efficacy endpoints.

17.1.3. Efficacy Analysis

Endpoints 1 and 2 are calculated with the following formula, respectively for Phases 1 and 2:

$100\% * ((X - Y) / (N - M))$, where

- N = Number of subjects who entered the Run-in period for the Phase.
- M = Number of subjects excluded during Run-in period due to non-RLS opioid withdrawal symptoms.
- Y = Number of subjects excluded during Run-in period primarily due to intolerable RLS symptoms.
- X = Number of subjects who complete Assessment period with no clinically significant worsening in Clinical Global Impression-Improvement scale (CGI-I) relative to Baseline, where a clinically significant worsening is defined by a score of 6 (Much worse) or 7 (Very much worse).

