Study Design	
The flowchart details the study design:
 
Opioid-treated RLS patients undergo Consent, screening, and NPNS training.They enter Phase 1, >=20% opioid dose reduction, which includes a NPNS 1-2 wk Run-in period and a NPNS 1-wk Assessment period. A CGI-I rating is taken during the assessment period. If CGI-I > 5, the patient is Not tolerated and the study ends. If CGI-I of 5 or less, they proceed to Phase 2, >=33% opioid dose reduction relative to baseline.Phase 2 follows the same structure: NPNS 1-2 wk Run-in period and NPNS 1-wk Assessment period. If CGI-I > 5, the patient is Not tolerated and the study ends. If CGI-I of 5 or less, they enter the Optional Extension Phase.The Optional Extension Phase involves NPNS 1-2 wk Run-in period and NPNS 1-wk Assessment period. If CGI-I > 5, the patient is Not tolerated and the study ends. 
An iterative opioid dose reduction is performed in conjunction with open-label NPNS administration. For each of the two step-downs in opioid dose (Phase 1 and Phase 2), a 1-2-wk run-in period is followed by a 1-wk assessment period. The run-in period is to ensure that any opioid withdrawal symptoms unrelated to RLS have resolved and to confirm the appropriate instructions for NPNS usage (e.g. timing and intensity). Study participation is terminated at the first phase that leads to a clinically significant

CONFIDENTIAL

 NOCTRIX HEALTH	Clinical Trial Investigational Plan, Protocol CT-03 (Opioid Reduction Study)	Document #: CT-2 (Previously CT-03) Rev: 4.0 (Superseded Rev C) CC#: 720 (Previously DCO #138) Effective: 09/24/2021
---	---	---

	
increase in RLS severity or is otherwise not tolerated. Participants who tolerate both phases may have the option of an extension phase involving a third reduction in opioid dose.

Study Population	
Adults with moderate-to-severe primary Restless Legs Syndrome (RLS) who are taking a stable dose of prescription opioids to treat RLS.

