13.1 Accounting for between-subjects variation in starting opioid dose

The study has been designed to account for between-subjects variation in the starting dose and quantal dose of opioid medication, while also allowing calculation of standardized efficacy endpoints. The opioid dose reduction process is complicated by that fact that there are quantal doses of opioid medication. For example, for methadone, which is commonly prescribed for RLS, the minimum pill size is 5mg and the quantal size is 2.5mg because pills can be broken in half.

All subjects initially participate in Phase 1, which involves the smallest reduction in opioid dose of greater than or equal to 20% of the starting dose. Subjects who tolerate Phase 1 without a clinically significant increase in RLS symptoms will advance to Phase 2, which involves the smallest additional reduction in opioid dose that also represents a total reduction of greater than or equal to 1/3 of the starting dose. Subjects who tolerate Phase 2 without a clinically significant increase in RLS symptoms will have the option to complete Phase 3, which involves an additional reduction in opioid dose. Once the subject completes a Phase where no further reduction is possible (e.g. a subject reaches 0mg in Phase 1 or 2), they will complete the study at the end of that Phase.

For example, in the case of methadone, the minimal quantal dose reduction is 2.5mg. Therefore, for methadone (**Table 4**):

- a subject on a 10mg starting dose would reduce to 7.5mg (25% reduction) in Phase 1 and 5.0mg (50% total reduction) in Phase 2. The endpoints related to $\geq 20\%$ reduction would be evaluated in Phase 1 and the endpoints related to $\geq 1/3$ reduction would be evaluated in Phase 2.
- a subject on a 7.5mg starting dose would reduce to 5.0mg (1/3 reduction) in Phase 1 and 2.5mg (2/3 total reduction) in Phase 2. The endpoints related to both $\geq 20\%$ reduction and $\geq 1/3$ reduction would be evaluated in Phase 1.
- a subject on a 5.0mg starting dose would reduce to 2.5mg (50% reduction) in Phase 1 and 0mg (100% total reduction) in Phase 2. The endpoints related to both $\geq 20\%$ reduction and $\geq 1/3$ reduction would be evaluated in Phase 1.
- a subject on a 2.5mg starting dose would reduce to 0mg (100% reduction) in Phase 1 and complete the study at the end of Phase 1. The endpoints related to both $\geq 20\%$ reduction and $\geq 1/3$ reduction would be evaluated in Phase 1.

CONFIDENTIAL

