17.1.1. Efficacy Endpoints

Endpoint 1 (Primary Endpoint): Percentage of subjects without a clinically significant increase in RLS symptoms (i.e. CGI-I score of 5 or less relative to baseline) during the first Phase involving an opioid dose reduction of $\geq 20\%$ relative to baseline.

Endpoint 2: Percentage of subjects without a clinically significant increase in RLS symptoms (i.e. CGI-I score of 5 or less relative to baseline) during the first Phase involving an opioid dose reduction of $\geq 1/3$ relative to baseline.

Endpoint 3: IRLS during the first Phase with an opioid dose reduction of $\geq 20\%$ relative to baseline.

Endpoint 4: IRLS during the first Phase with an opioid dose reduction of $\geq 1/3$ relative to baseline.

CONFIDENTIAL

 NOCTRIX HEALTH	Clinical Trial Investigational Plan, Protocol CT-03 (Opioid Reduction Study)	Document #: CT-2 (Previously CT-03) Rev: 4.0 (Superseded Rev C) CC#: 720 (Previously DCO #138) Effective: 09/24/2021
---	---	---

Endpoint 5: Maximal percentage reduction in opioid dose relative to baseline associated with a CGI-I score of 5 or less, averaged across subjects.

Of the 5 efficacy endpoints, only Endpoint 5 considers data during the Extension phase.

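### Endpoint 2 is calculated on Phase 2 entrants, so subjects who failed for RLS worsening at a Phase 1 cut below one third drop out of its denominator, and 17.1.3 conflicts with 13.1 on where it is evaluated

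*Combined protocol and SAP*

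**What the plan says.** The endpoint list in 17.1.1 (repeated in the synopsis) opens "Endpoint 2: Percentage of subjects without a clinically significant increase in RLS symptoms" and ties it to the first phase in which the cut reaches 1/3. It names no restriction to subjects who passed an earlier phase.

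Section 17.1.3 gives one formula, 100% × (X − Y)/(N − M), and states: "Endpoints 1 and 2 are calculated with the following formula, respectively for Phases 1 and 2". The denominator starts from this count: "N = Number of subjects who entered the Run-in period for the Phase". From it the plan takes M, the run-in exits caused by opioid withdrawal other than RLS. In the numerator, X counts those who finish the assessment week with a CGI-I of 5 or less, and Y, the run-in exits caused mainly by RLS, is subtracted from X.

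Entry to Phase 2 is selective. Section 13.1 says "Subjects who tolerate Phase 1 without a clinically significant increase in RLS symptoms will advance to Phase 2", and the synopsis adds "Study participation is terminated at the first phase that leads to a clinically significant" worsening of RLS. Section 13.2 counts a run-in RLS dropout only for the phase in which the subject stops. Nothing carries a Phase 1 failure into Endpoint 2.

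The worked methadone examples in 13.1 evaluate Endpoint 2 in Phase 1 for a subject whose Phase 1 cut already reaches 1/3. Section 17.1.3 has no such provision.

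**The concern.** Section 3 asks whether NPNS allows a clinically meaningful opioid reduction, and Endpoint 2 is the only responder endpoint for the larger cut. A reader will take it as the share of treated subjects who tolerated a cut of at least 1/3. As calculated, it is the share among those already shown to tolerate a smaller cut. In a single-arm, open-label study no control group would expose that selection, and with 20-40 subjects a few Phase 1 failures move the figure noticeably. The report could show the deeper cut as better tolerated than the shallower one only because earlier failures were removed.

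The populations also depend on which section is followed. Under 13.1, some subjects enter Endpoint 2 unselected, through Phase 1, and others only if they passed Phase 1. Under literal 17.1.3, everyone is judged in Phase 2, and a subject who reaches zero dose in Phase 1 is never counted.

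**Working it through.** The plan states no expected rate, power or target for Endpoint 2, so there is no figure of its own to reproduce. The dose rule can be checked; the tolerance counts below are assumptions.

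**1. Where 1/3 is first reached.** Apply the 13.1 rule (smallest 2.5 mg-step cut of at least 20%) to the starting doses in Table 4:

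| Start (mg) | Phase 1 cut | Endpoint 2 evaluated in |
|---|---|---|
| 20 | 25% | Phase 2 |
| 17.5 | 28.6% | Phase 2 |
| 15 | 33.3% | Phase 1 |
| 12.5 | 20% | Phase 2 |
| 10 | 25% | Phase 2 |
| 7.5 | 33.3% | Phase 1 |
| 5 | 50% | Phase 1 |
| 2.5 | 100% | Phase 1 (no Phase 2) |

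This reproduces the four examples in 13.1 (10, 7.5, 5 and 2.5 mg). Read literally, 17.1.3 drops the 2.5 mg starter, who finishes at the end of Phase 1.

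**2. Literal 17.1.3, M = Y = 0.** Assume 40 start, 24 tolerate Phase 1 and enter Phase 2, and 17 of those tolerate Phase 2.

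- Endpoint 1 = 24/40 = 60%
- Endpoint 2 as written = 17/24 = 70.8%
- Same successes over all starters = 17/40 = 42.5%

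In this setting the written rate is the all-starter rate divided by the Phase 1 pass rate: 42.5%/0.60 = 70.8%. It exceeds Endpoint 1 whenever the pass rate among Phase 2 entrants exceeds the Phase 1 pass rate. For Phase 1 pass rates of 50-90% and Phase 2 pass rates of about 60-90%, the excess runs from about 6 points (22/36 = 61.1% against 22/40 = 55.0%) to 45 points (18/20 = 90.0% against 18/40 = 45.0%).

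**3. Reading by 13.1.** Assume 20 subjects reach 1/3 in Phase 1 and 12 tolerate it; the other 20 go 20 → 12 → 8.

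- Endpoint 2 = (12 + 8)/(20 + 12) = 20/32 = 62.5%
- Over all starters = 20/40 = 50%

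The ratio is 1.25, not the 1/0.60 = 1.67 of step 2. Endpoint 2 is still above Endpoint 1 (24/40 = 60%).

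**4. Effect of subtracting Y.** A subject excluded during run-in cannot be in X, so X − Y penalises run-in RLS failures twice. Take step 2 and let all 7 Phase 2 failures occur in the run-in:

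- As written: (17 − 7)/24 = 41.7%, just below 17/40 = 42.5%
- Same numerator over all starters: (17 − 7)/40 = 25.0%

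With X = 14 and Y = 8 the gap widens: (14 − 8)/24 = 25.0% against 14/40 = 35.0%. With M = 0, the written figure exceeds X over all starters only if Y/X is below the Phase 1 failure proportion. Here that is 1 − 24/40 = 0.40, and 7/17 = 0.41 is already above it. For a fixed positive numerator the smaller denominator always inflates.

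**The case against.** The strongest reply is that the denominator is disclosed. A per-phase conditional rate is a legitimate estimand in a step-down design, the study is exploratory, and no comparison of Endpoint 2 with Endpoint 1 is planned. The first part stands to this extent: the conditional rate is worth reporting. But the endpoint's name carries no condition, and 13.1 and 17.1.3 do not define the same rate.

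Three stronger inferences are tempting, and the documents do not support them.

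- *Endpoint 2 is always overstated.* Step 4 shows that the Y subtraction can cancel or reverse the net effect. Section 13.2 expressly provides for run-in RLS exits, so Y cannot be assumed to be zero.
- *The overstatement is always 1/(Phase 1 tolerance rate).* That holds only for literal 17.1.3 with M = Y = 0. Under 13.1 it is diluted by subjects who reach 1/3 in Phase 1. At 90% Phase 1 tolerance even the literal factor is only 1.11.
- *The study's success claim is at risk.* The only efficacy pass rule (17.1.5) is Endpoint 1 above 50%. Endpoint 2 has no success criterion.

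It is also fair to object that the stopping rule does not itself say that a subject who worsened at the smaller cut would fail the larger one. Counting such a subject as a failure is an assumption and should be stated as one.

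**Conclusion.** The point holds as a moderate one. Under either reading, a subject who fails for RLS worsening at a Phase 1 cut below 1/3 never enters the Endpoint 2 denominator. The reported figure is therefore a rate conditional on tolerating Phase 1, and it can exceed Endpoint 1. Separately, 17.1.3 and 13.1 disagree on the phase in which Endpoint 2 is evaluated.

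The size cannot be fixed from the documents, which give neither tolerance rates nor a dose mix. With 40 starters, 60% Phase 1 tolerance and no run-in RLS exits, the examples give excesses of 28.3 points (70.8% less 42.5%) under literal 17.1.3 and 12.5 points (62.5% less 50%) under 13.1. What is certain is the direction of the denominator effect, not the direction of the net figure.

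**What to change.** In 17.1.3:

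- Define Endpoint 2 over all subjects who entered the Phase 1 run-in, leaving out non-RLS withdrawal exits in either phase, as the plan already intends.
- Count a subject who stopped for RLS worsening in Phase 1 as not achieving Endpoint 2.
- Evaluate each subject in the phase where a cut of 1/3 is first reached, as 13.1 does, and drop the fixed link between Endpoint 2 and Phase 2.
- Use the number of successes as the numerator, without subtracting Y. Endpoint 1 shares the formula, so the two numerators should be aligned. Otherwise the revised Endpoint 2 could still exceed Endpoint 1: with 40 starters, X = 24 and Y = 8 in Phase 1 and 19 successes in Phase 2, it would be 19/40 = 47.5% against (24 − 8)/40 = 40%.
- Give one rule for other exits, such as device intolerance or personal reasons, and reconcile it with 13.2. At present 17.1.3 leaves these subjects in N, while 13.2 keeps their exit scores out of the efficacy analysis. The 13.2 wording that counts RLS dropouts only for their own phase needs a matching edit.
- Report the Phase 2 entrant rate as supportive, labelled as being among subjects who tolerated Phase 1.

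The cost is wording in 17.1.3 and 13.2, with no new data. Endpoint 2 will usually look less favourable, and it will rest on the assumption that a subject who worsened at the smaller cut would not have tolerated the larger one. Reporting both rates lets the reader judge that assumption.

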Study Participation Duration	
Study participation duration in the main study period will typically be 4-6 weeks:
 
Phase 1:
 
1-2 wk run-in
 
1-wk assessment
 
Phase 2:
 
1-2 wk run-in
 
1-wk assessment
 
Study duration may be somewhat shorter, such as if Phase 1 is not tolerated.
 
Study duration may be longer, such as if run-in period is extended or depending on scheduling constraints.
 
The optional extension phase (Phase 3) will last an additional 2-3 weeks.

Study Interventions	
1. NTX Neuromodulation System (NPNS) programmed to ACTIVE mode
 
2. Dosage of prescription opioid medication will be iteratively reduced. Dosage reduction will be terminated if withdrawal symptoms become intolerable.

Maximum Study Duration	
The study will be completed a maximum of 18 months after the study opens to enrollment.

Total Number of Subjects	
20-40 subjects will be enrolled in the primary study
 
Up to 10 additional subjects may be enrolled in a pilot phase
 
Total enrollment: 20-50

Number of Sites	
Up to 4 Clinical sites will participate

Study Endpoints	
Efficacy

CONFIDENTIAL

All information contained in this document is confidential and is the sole property of Noctrix Health, Inc.
 Any reproduction in part or whole without the written permission of Noctrix Health, Inc. is prohibited.

 NOCTRIX HEALTH	Clinical Trial	Document #: CT-2 (Previously CT-03) Rev: 4.0 (Superseded Rev C) CC#: 720 (Previously DCO #138) Effective: 09/24/2021
---	-----------------------	---

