13.2 Run-in and Assessment periods

[figure not shown]
Each Phase involves a 1-2 week run-in period followed by a 1-week assessment period. Assessment periods are primarily designed for endpoint evaluation. Run-in periods are designed for two reasons: (i) to provide a run-in phase to optimize instructions for NPNS device self-administration (e.g. timing and intensity) and (ii) so that any opioid withdrawal symptoms unrelated to the RLS condition resolve prior to the assessment period. Each run-in period will last a minimum of 1-week and a maximum of 2-weeks.

The investigator is permitted to adjust the instructed schedule of opioid medication and/or NPNS usage during a Step-Down based on clinical evaluation of response to opioid treatment and NPNS.

CONFIDENTIAL

All information contained in this document is confidential and is the sole property of Noctrix Health, Inc.
Any reproduction in part or whole without the written permission of Noctrix Health, Inc. is prohibited.

Figure 1. Flowchart of Run-in and Assessment periods for Phases 1 & 2

Additionally:

[figure not shown]
- If clinically significant opioid withdrawal symptoms unrelated to RLS become intolerable during the run-in period for a given Phase, participation will be discontinued and data from the subject will not count towards the efficacy endpoints for that Phase.
- If opioid withdrawal symptoms related to RLS become intolerable at any point during a run-in period, participation will be discontinued and the subject will count towards the efficacy endpoints for that Phase.
- The investigator may decide that participation should be discontinued at any time if there are excessive opioid withdrawal symptoms, even if those symptoms are tolerable.
- If opioid withdrawal symptoms become intolerable mid-week during a run-in period, participation will be discontinued.
- In all cases, efficacy outcome measures CGI-I and IRLS will be assessed at study exit but will not be included in analysis of the efficacy endpoints unless opioid withdrawal symptoms related to RLS was the primary reason for discontinuation.
- The Extension Phase is optional and requires approval by both the investigator and the participant. The structure of this phase is similar phases 1 and 2.

CONFIDENTIAL

All information contained in this document is confidential and is the sole property of Noctrix Health, Inc.
 Any reproduction in part or whole without the written permission of Noctrix Health, Inc. is prohibited.

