17.1. Efficacy

In the absence of an adjunctive treatment, a reduction in opioid dose will cause an increase in RLS symptoms. The efficacy of NPNS will be assessed by its capacity to prevent this increase in RLS symptoms. Subjects who discontinue due to nonspecific opioid withdrawal symptoms will not be included in the efficacy analysis but will be considered in the safety analysis. Efficacy endpoints will be calculated during the Assessment period except in cases of dropout during the run-in period(s); Section 13.2 describes how efficacy endpoints will be calculated in cases of dropout during the run-in period(s).

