17.1.5. Criterion for Success

If Endpoint 1 is greater than 50 percent, then the study will pass the Primary Efficacy endpoint.

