17.2. Safety

Safety will be assessed primarily based on response to NPNS. However, the proportion of subjects excluded due to non-RLS opioid withdrawal symptoms will also be considered in the safety analysis.

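### Sections 17.1 and 17.1.3 treat Assessment-week exits for non-RLS withdrawal differently, and removing run-in exits lets the primary criterion pass with under half of starters succeeding

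*Combined protocol and SAP*

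**What the plan says.** The primary endpoint is the percentage of subjects without a clinically significant increase in RLS symptoms at the first opioid reduction of at least 20%. Section 17.1.3 computes it as 100% x (X - Y)/(N - M), with these terms:

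- N is everyone who started the run-in of that Phase.
- The term taken out of the denominator is given as "M = Number of subjects excluded during Run-in period due to non-RLS opioid withdrawal symptoms".
- Y, taken off the numerator, is the count of run-in exits put down mainly to RLS symptoms that could not be tolerated.
- X counts those who complete the Assessment period with a CGI-I below 6.

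Section 17.1 states the exclusion without reference to period: "Subjects who discontinue due to nonspecific opioid withdrawal symptoms will not be included in the efficacy analysis". It points to section 13.2 only for dropout in the run-in.

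Section 13.2 has one bullet on subjects who leave because non-RLS withdrawal becomes intolerable in the run-in; they do not count towards efficacy for that Phase. A later bullet says that exit CGI-I and IRLS scores "will not be included in analysis of the efficacy endpoints unless opioid withdrawal symptoms related to RLS was the primary reason for discontinuation".

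The decision rule in section 17.1.5 is: "If Endpoint 1 is greater than 50 percent, then the study will pass the Primary Efficacy endpoint". The synopsis gives the size: "20-40 subjects will be enrolled in the primary study". On safety, section 17.2 says that "the proportion of subjects excluded due to non-RLS opioid withdrawal symptoms will also be considered in the safety analysis".

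**The concern.** An Assessment-week exit for non-RLS withdrawal is not in X, because the subject did not complete the period. It is not in M or Y either, because both are limited to the run-in. Under 17.1.3 it therefore stays in N as a non-success. Under 17.1 the same subject is taken out of the analysis. The plan gives two primary percentages for the same data, and the criterion is a bare point estimate in a small sample.

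A second matter is separate from the conflict. The section 3 objective asks whether the response to NPNS is enough to allow a clinically significant opioid reduction. A subject who stops for withdrawal has not achieved that reduction, yet leaves the denominator if the exit is in the run-in. The four success criteria are the primary percentage (17.1.5), device-related adverse events (17.2.3), withdrawal for device intolerability (17.3) and compliance (17.4). None sets a limit on how many subjects may leave this way.

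**Working it through.** **Inputs.** N of 20 to 40 (synopsis); pass if the percentage exceeds 50% (17.1.5); formula and terms from 17.1.3. The documents give no sample-size derivation, expected exit rate or cap on M, so there is no stated figure to reproduce. Let A be the number of Assessment-week exits for non-RLS withdrawal.

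**1. The conflict.** 17.1.3 gives (X - Y)/(N - M). 17.1 gives (X - Y)/(N - M - A). The verdicts differ when (N - M - A)/2 < X - Y <= (N - M)/2.

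- N=20, M=0, A=1, X=10, Y=0: 10/20 = 50.0% (fail) against 10/19 = 52.6% (pass).
- N=20, M=4, A=2, X=8, Y=0: 8/16 = 50.0% (fail) against 8/14 = 57.1% (pass).
- N=40, M=8, A=3, X=16, Y=0: 16/32 = 50.0% (fail) against 16/29 = 55.2% (pass).

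With A=1 the inequality holds only if the 17.1.3 result is exactly 50%. The window widens as A grows.

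**2. Passing with fewer than half of starters succeeding.** For even N, the largest X below half is N/2 - 1. The formula then passes if 2(N/2 - 1 - Y) > N - M, that is, if M > 2 + 2Y. The smallest M is 3 + 2Y:

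| N | Y | M | X | (X - Y)/(N - M) | X/N |
|---|---|---|---|---|---|
| 20 | 0 | 3 | 9 | 9/17 = 52.9% | 9/20 = 45.0% |
| 20 | 1 | 5 | 9 | 8/15 = 53.3% | 45.0% |
| 20 | 2 | 7 | 9 | 7/13 = 53.8% | 45.0% |
| 40 | 0 | 3 | 19 | 19/37 = 51.4% | 19/40 = 47.5% |
| 40 | 1 | 5 | 19 | 18/35 = 51.4% | 47.5% |
| 40 | 2 | 7 | 19 | 17/33 = 51.5% | 47.5% |

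At Y=3 the smallest M is 9. That is impossible at N=20 (9 + 3 + 9 = 21 subjects) but possible at N=40. For odd N the same algebra gives M = 2 + 2Y; for example N=21, M=2, X=10, Y=0 gives 10/19 = 52.6% against 10/21 = 47.6%.

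**3. How often, under assumed rates.** The documents give no rates, so these are illustrations. Assume true success in 45% of starters, Y=0, and run-in non-RLS exit rates of 5%, 10%, 20% and 30%.

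- N=20: the probability of passing by the formula is 0.36, 0.45, 0.65 and 0.83, against 0.25 if X/N had to exceed 50%.
- N=40: 0.34, 0.47, 0.73 and 0.93, against 0.21.
- With 5% RLS exits added, the values at the 20% rate fall to 0.47 (N=20) and 0.48 (N=40).

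**4. Comparing the percentages.** Subjects in Y are already in N and not in X, so subtracting Y counts them twice. Moving from the primary formula to X/N therefore makes two changes at once. For N=20, X=12, Y=3, M=1:

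- primary: (12 - 3)/19 = 47.4%
- X/(N - M): 12/19 = 63.2%
- X/N: 12/20 = 60.0%

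Only the last two isolate the effect of removing M.

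**The case against.** The strongest defence is that excluding non-RLS withdrawal is a disclosed choice. Endpoint 1 measures RLS worsening, and the run-in exists partly so that unrelated withdrawal symptoms resolve before assessment. Assessment-week exits should then be few, and section 6.2.1 expects a low risk of withdrawal symptoms. The study also calls itself exploratory. This stands as a reason to keep M in the primary formula. It does not settle which of the two rules applies when an Assessment-week exit occurs, and no rate supports the low expectation.

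Three stronger readings are tempting and not supported:

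- A reader might take the exit-score sentence in 13.2 as a third denominator rule. Its subject is the CGI-I and IRLS measurements taken at exit, so it governs which scores are used, not who is in N. The 13.2 bullet on run-in exits agrees with M.
- A reader might infer that these exits are not counted at all. They are prespecified outputs (Safety Endpoints 4, 7 and 8, and synopsis Safety Endpoint 3), and 17.2.2 tabulates withdrawal-related adverse events. What is missing is a threshold.
- A reader might infer that the study is likely to pass while most starters fail. The documents show only that it can, and each RLS exit in the run-in raises the number of non-RLS exits needed by two.

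**Conclusion.** The point holds as a contradiction between 17.1 and 17.1.3 confined to Assessment-week exits for non-RLS withdrawal. One such exit changes the verdict only at the boundary, as in 50.0% against 52.6% at N=20; several widen the range of results affected.

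Separately, the formula can pass with fewer than half of starters succeeding. At N=20 or N=40 this takes at least three run-in exits when Y=0 (15% and 7.5% of starters), five when Y=1 and seven when Y=2. These minimum counts are arithmetic from the plan's own rule and need no assumed rate. The pass probabilities rest wholly on assumed rates.

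Both matters should be corrected before analysis. Neither invalidates the choice of primary endpoint.

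**What to change.** - Align 17.1 with 17.1.3 and 13.2: only run-in exits for non-RLS withdrawal are M. Every other run-in entrant, including an Assessment-week withdrawal exit, stays in N as a non-success. This keeps the sponsor's formula and matches the 13.2 run-in bullet.
- State in 13.2 that the exit-score sentence concerns which measurements are used, not the denominator.
- Prespecify a supporting percentage X/N over all run-in entrants, with an exact confidence interval, in which RLS exits and non-RLS exits each count once as non-successes. Report whether it exceeds 50%.
- Show X/N beside X/(N - M) and the primary formula, so that the effect of removing M is not confused with that of subtracting Y.

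The cost is a few sentences and one or two lines of output. X/N can never be more favourable than X/(N - M), but when Y>0 it may be higher or lower than the primary percentage, and the report should say so. No change to any clinical discontinuation rule is proposed.
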